## Procedures

All participants in both groups will make a total of 3 visits over a 16-week period. The 2nd visit is at week 4 and 3rd visit at week 16 after initial visit. At each visit, all patients will have a blood test for A1c, CMP, CBC, fasting lipid and measurements of body weight, height, blood pressure, and heart rate, answered adverse reaction questions and completed the Diabetes Medications Satisfaction (DM-SAT) Questionnaire form.

At first visit, the following changes will be made in intervention group:

- (1) All prandial insulin injections (Humalog, Novolog, Apidra, Novolin R or Humulin R) will be discontinued.
- (2) Basal insulin (NPH, Lantus, Levemir, Toujeo or Tresiba) will be continued at 80 % of the home dose. The dose will be gradually increased until the patient is back on the home dose (the dose that the patient has been taking at home prior to the enrollment) or fasting BG of 80-130mg/dl was achieved by using the self-titration regimen. (Attachement#1)
- (3) If the patient is on pre-mixed insulin 2-3 times daily, it will be switched to a basal insulin alone and Glargine was given at 40% of total daily dose of pre-mixed insulin. The dose will be gradually increased until fasting BG of 80-130mg/dl is achieved by using the self-titration regimen. (Attachement#1)
- (4) Metformin at home dose will be continued, but other non-insulin diabetes medications will be discontinued. If the patient is not on metformin, then Metformin ER will be started at 500mg daily with a meal for 2 weeks and then 1000mg daily as a maintenance dose if tolerated.
- (5) Both SGLT2i, Empagliflozin 10 mg or 12.5mg once daily, and GLP1 RA, Dulaglutide 0.75mg subcutaneously once weekly, will be added to metformin and a basal insulin.

The patients will be trained on the injection technique of the once-weekly GLP1 RA and given information on potential side effects, risk and benefits of all new medications in detail, hypoglycemia management and the self-titration regimen for the basal insulin.

In the control group, the patients will be advised to remain on MDI and to have the usual and standard care through the primary care provider. They will also be advised to gradually increase the basal insulin until fasting BG of 80-130mg/dl is achieved by using the self-titration regimen as in the intervention group. (Attachement#1)

The patients in both groups will be advised to monitor FPGs daily at minimum.

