A research coordinator will make a phone call to all participants in both groups at week 1, 2, 8, and 12 to review fasting glucose measurements, ask for possible adverse events, incidents of hypoglycemia, and any change in medication.

At each visit, the patients will be questioned for adverse events (nausea, vomiting, diarrhea, headache, acute pancreatitis, bacterial or fungal genito-urinary tract infection, severe hypoglycemia with blood glucose <40, mild hypoglycemia with BG 41-69, diabetes ketoacidosis, any hospitalization for hyper or hyper-glycaemia).

At 2nd visit, Empagliflozin and GLP1 RA, Dulaglutide will be increased to maximum doses of 25mg and 1.5mg respectively if the patient tolerated the starting dose and if the additional glycemic control is required.

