## Outcome measurements

The primary outcome is the change in A1c at the end of study period at week 16 and secondary outcomes are the changes in fasting blood glucose, weight, blood pressure, heart rate, fasting

lipids, serum sodium and potassium, serum creatinine, liver enzymes, CBC and Diabetes Medications Satisfaction (DM-SAT) scores at week 16.

Treatment satisfaction will be measured using the Diabetes Medication Satisfaction Tool (DM-SAT).

The DM-SAT measures satisfaction with the patient's diabetes medications regimen. The instrument consists of 16 items which create 4 subscales (3 items for wellbeing, 3 items for medical control, 5 items for lifestyle, and 5 items for convenience) and a total score. Responses are summed and converted to a score from 0 to 100 for each subscale and overall, with higher scores representing more satisfaction.

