### **Statistical Analysis:**

We will attempt to recruit and consent 20 patients in each arm that was calculated to provide an 80% statistical power at a 0.05 alpha in this continuous endpoint, two independent sample study.

The calculation was based on the following:

A mean Hemoglobin A1c of  $8.5 \pm 1\%$  at the initiation of the study period. In the treatment group we anticipate a decline in Hemoglobin A1c of 12-15% by the end of the study period. The standard deviation for the mean A1c was derived from the literature (Glucagon-Like Peptide 1 Receptor Agonist or Bolus Insulin With Optimized Basal Insulin in Type 2 Diabetes. Michaela Diamant Et al. Diabetes Care October 2014 vol. 37 no. 10. 2763-2773)

The data will be analyzed by using SPSS or similar software. Significance testing will be conducted at the two-sided 5% level. Continuous variables will be examined for normality and if assumption is met, differences in mean values will be tested using Student's t test an analysis of variance (ANOVA). If not normally distributed, non-parametric procedures will be used, including Wilcoxon rank Sum test. Categorical data will be analyzed using Fisher's exact test and Chi square analysis. Since before/after comparisons will also be performed on the same study patients, we will utilize paired t tests and McNemar's chi-square test.

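### The primary test is complete-case by default, does not adjust for baseline A1c and leaves the week-4 A1c unused; response-linked dropout in the step-down arm could therefore favour step-down

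*Combined protocol and SAP*

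**What the plan says.** Outcome measurements defines the endpoint: "The primary outcome is the change in A1c at the end of study period at week 16". Statistical Analysis gives the test: "differences in mean values will be tested using Student's t test", or analysis of variance. The fallback reads "If not normally distributed, non-parametric procedures will be used, including Wilcoxon rank Sum test".

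Procedures schedules three visits for everyone, at baseline, week 4 and week 16, and states "At each visit, all patients will have a blood test for A1c". A week-4 A1c is therefore planned in both arms. Neither Outcome measurements nor Statistical Analysis uses it.

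Also under Procedures, only the step-down arm stops prandial insulin and has two new agents added. Raising their doses at week 4 depends partly on tolerance ("if the patient tolerated the starting dose"). The Design section describes the trial as open-label.

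The documents give no analysis set, missing-data method, expected dropout or dropout allowance. They do not say explicitly whether a patient who stops the assigned drugs still attends at week 16.

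**The concern.** A two-sample t test, an analysis of variance or a rank-sum test on week-16 change can use only patients who have that value. With nothing else in the plan to retain the others, the comparison becomes one of completers, and randomisation protects it only if the missing patients resemble those who stay.

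There is a design reason to doubt that resemblance here. The arms differ in what is withdrawn, what is started and what side effects are likely, and patients know their assignment. A step-down patient who leaves early may have given up prandial insulin without gaining the full effect of the new regimen. If such patients would have had a worse week-16 A1c, their absence flatters step-down. With 20 per arm, a 20-30% loss is 4 to 6 patients, enough to move the primary estimate.

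This goes beyond missing detail. The method the plan does state is weaker than one that needs only measurements already scheduled.

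**Working it through.** **Inputs from the plan.** 20 per arm ("We will attempt to recruit and consent 20 patients in each arm"), two-sided 5%, 80% power, baseline A1c 8.5 with SD 1, and a 12-15% decline in the step-down arm, which is 8.5 × 0.12 = 1.02 to 8.5 × 0.15 = 1.275 points. No control-arm change is given, so it is taken as 0.

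**The plan's own figure.** The size is described as "calculated to provide an 80% statistical power at a 0.05 alpha". Taking SD 1 for the quantity compared, n per arm = 2(1.96 + 0.842)² / d².
- d = 1.02: 15.70 / 1.040 = 15.1, so 16 (17 with the t distribution).
- d = 1.275: 15.70 / 1.626 = 9.7, so 10 (11 with t).

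The stated 20 is not reproduced, but it is on the safe side. At d = 1.02, power by the t distribution is 88.2% with 20 v 20, 84.0% with 16 v 20 and 79.7% with 16 v 16. Losing about 20% costs little power against the target, so the issue is bias.

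**Bias of the completer comparison.** Let q be the share of the step-down arm that is missing, and g the dropouts' week-16 change minus the completers' change. The mean over all randomised patients is the completer mean plus q × g, so the completer analysis is off by −q × g (negative favours step-down). Both q and g are assumptions.

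| g (points) | q = 20% | q = 30% |
|---|---|---|
| −0.5 | +0.10 | +0.15 |
| 0 | 0 | 0 |
| +0.5 | −0.10 | −0.15 |
| +1.0 | −0.20 | −0.30 |

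**Simulation with dropout linked to week-4 response.** Everything here is assumed: SD 1 at each visit; correlations 0.80 (baseline and week 4), 0.75 (weeks 4 and 16) and 0.55 (baseline and week 16); 5% random control dropout; step-down dropout after week 4, more likely the worse the week-4 change; true difference 1.02; 4,000 trials of 20 per arm. A rerun with the log-odds of dropout rising by 1 per SD of week-4 change also gave t-test means of 1.13 and 1.19.

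| Mean estimate | 20% dropout | 30% dropout |
|---|---|---|
| Completer t test | 1.125 (bias 0.10) | 1.191 (bias 0.17) |
| Completers, baseline-adjusted | 1.102 (bias 0.08) | 1.153 (bias 0.13) |
| Likelihood model using week 4 | 1.019 | 1.015 |
| t-test type I error, no true effect | 6.8% | 8.2% |

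Over three sets of correlations the t-test bias was 0.11-0.16 at 20% and 0.16-0.24 at 30%, with type I error of 5.8-7.6% and 7.0-11.3%. A hand check agrees. With a standard error of 0.33, a bias of 0.17 is 0.515 standard errors, and P(Z > 1.96 − 0.515) + P(Z < −1.96 − 0.515) = 0.074 + 0.007 = 8.1%. A bias of 0.24 gives 0.109 + 0.004 = 11.2%.

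**Precision.** The standard error is about 0.28-0.30 for the model against 0.31-0.33 for the t test. Most of the gain comes from baseline adjustment (0.292 at 20% dropout). The week-4 value mainly removes bias.

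**Where the link is absent or unobserved.** If dropout is unrelated to A1c, the t test is unbiased and its rejection rate stays near 5%. If dropouts worsen by 1.0 point only after leaving, unrelated to week 4, the t test and the week-4 model are both off by about 0.2 at 20% dropout and 0.3 at 30%.

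**The case against.** Three stronger readings are tempting, and the documents support none of them.

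- **That the plan excludes patients without a week-16 A1c.** It is silent. Exclusion is what the named tests do when nothing else is specified.
- **That tolerability dropout would favour step-down.** No section gives a dropout rate or ties intolerance to glycaemic response. Nausea unrelated to A1c gives no bias, and dropouts who would have done better reverse it. Selective loss in the control arm is possible too. The simulated bias comes from the assumed link to week-4 response.
- **That a model using week 4 cures the problem.** Dropout driven by the observed week-4 value is exactly the situation in which that model is unbiased, so its good showing there is built in. It does not cover patients who worsen only after leaving, and gives little help for those lost before week 4.

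It is also fair to say that stopping a drug differs from missing a visit. Procedures schedules three visits for all participants without making them conditional on staying on treatment, and adds telephone calls at weeks 1, 2, 8 and 12. A patient who stops but attends week 16 is analysed. Finally, a bias of 0.10-0.17 on a true 1.02 would not overturn a result of the planned size.

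What stands is that the default is complete-case, the week-4 A1c is unused, and a better method is available from data already planned.

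**Conclusion.** The point holds as a conditional one. As written, the primary analysis has no analysis set or missing-data method, is complete-case by default, ignores baseline A1c except through the subtraction, and leaves the week-4 A1c unused. Under an assumed 20-30% step-down dropout linked to week-4 response, the bias towards step-down is about 0.1-0.25 points. Two-sided type I error is about 7-11%, and as low as 5.8% in the mildest setting tried. The bias is zero if dropout is unrelated to A1c.

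The dropout rates, the correlations and the form of the dropout link are all assumptions; the plan supplies none of them. The direction is plausible from the design but not established. The change is worth making before data are seen, because it costs little and removes a later choice in an open-label trial.

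**What to change.** In Statistical Analysis and Procedures:

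1. State that all randomised patients are analysed in their assigned arm.
2. State that the week-16 visit and A1c, already scheduled for all participants, are obtained even if study drugs are stopped. This reduces missing data whatever the mechanism.
3. Make the primary analysis one repeated-measures model of A1c at weeks 4 and 16, with terms for arm, visit, arm-by-visit, baseline A1c and baseline-by-visit, and an unstructured covariance. Report the week-16 difference between arms with its 95% CI.
4. Keep the completer t test as a sensitivity analysis.
5. Add a missing-not-at-random sensitivity analysis that gives progressively unfavourable week-16 values to missing step-down patients. The completer t test does not probe that case.

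The cost is a few sentences and a standard mixed model in the software already named, with no extra visits, tests or patients. The downside is a missing-at-random assumption, which item 5 is there to test, and slightly more complex reporting.

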## Study Protocol

### Is the stepping-down approach a better option than multiple daily injections in patients with chronic poorly controlled diabetes on advanced insulin therapy?

#### **Methods and Materials:**

This study is an interdepartmental collaborative study among the Department of Internal Medicine, Department of Family & Community Medicine (UCSF Fresno), Sierra Vista Family Medicine Residency Program and Division of Endocrinology.

The study will be conducted at the following multiple locations in order to maximize the patient recruitment:

- (1) Internal medicine clinic at Derian Koligian ambulatory care center (ACC)
- (2) Family practice medicine clinic at ACC
- (3) Endocrine clinic at ACC
- (4) Internal medicine clinic at University Medicine Associates in East medical Plaza
- (5) Endocrine clinic at University Medicine Associates in East medical Plaza
- (6) Sierra Vista clinics

The patients will be recruited during the first 12 months of the study or until the predetermined sample size is reached, whichever comes first.

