## Design

This is the prospective, randomized, open-label, controlled, parallel-group study. Patients will be allocated 1:1 to either intervention (i.e. Step-Down) or control (MDI) group by using block randomization with computer-generated random sequence from <http://www.randomization.com>.

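### Does the plan need a sentence naming the between-arm difference in A1c change as primary and the before/after tests as supportive?

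*Combined protocol and SAP*

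**What the plan says.** The title question in the protocol is comparative: "Is the stepping-down approach a better option than multiple daily injections". The Design section reads "This is the prospective, randomized, open-label, controlled, parallel-group study", and adds that "Patients will be allocated 1:1 to either intervention (i.e. Step-Down) or control (MDI) group".

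Under Outcome measurements, "The primary outcome is the change in A1c at the end of study period at week 16". That sentence names neither an arm nor a contrast.

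The Statistical Analysis section sizes the trial for a continuous endpoint in two independent samples, with 80% power at alpha 0.05: "We will attempt to recruit and consent 20 patients in each arm". The inputs are a baseline A1c of 8.5 with SD 1, and one effect: "In the treatment group we anticipate a decline in Hemoglobin A1c of 12-15% by the end of the study period". No change is given for the control arm.

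For continuous variables the section names Student's t test or ANOVA, with the Wilcoxon rank sum test if normality fails. It then closes with: "Since before/after comparisons will also be performed on the same study patients, we will utilize paired t tests and McNemar's chi-square test". It does not say which outcomes or arms these paired tests cover, or whether they are supportive.

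**The concern.** A change in A1c can be analysed as a paired difference within an arm or as a difference in change between arms, and no sentence says which one decides the trial. The only quantified effect is itself a fall from baseline in the treatment group. A1c is measured at every visit in both arms, so a paired test of the primary endpoint can be run.

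A fall from baseline in step-down would not show that step-down beats MDI. Patients enter with A1c above 8%, so some fall through regression to the mean is likely in both arms. Control patients also intensify basal insulin: "They will also be advised to gradually increase the basal insulin until fasting BG of 80-130mg/dl is achieved by using the self-titration regimen". If the paired result were taken as the answer, step-down could be called better when the randomised comparison shows no difference.

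**Working it through.** **1. Which contrast does the plan imply?** Five features bear on this.

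- The title question compares step-down with MDI, which a within-arm test cannot answer.
- Patients are randomised 1:1 to parallel groups.
- The sample size is for two independent samples with a continuous endpoint. The only endpoint in that calculation is A1c, so the primary endpoint is tied to a two-sample test.
- The non-parametric fallback named is the rank sum test, which is also for independent samples.
- The before/after comparisons come last and are introduced with the word also.

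All five agree, and nothing in the document makes a paired test decisive.

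**2. The plan's sample size.** A 12% to 15% relative decline from 8.5 is 8.5 × 0.12 = 1.02 to 8.5 × 0.15 = 1.275 points. With SD 1, no change in control (assumed) and a two-sided 5% two-sample t test, 80% power needs 17 per arm at 1.02 and 11 at 1.275. The stated 20 per arm is therefore not reproduced. It is larger than these inputs require, and gives power of 0.882 and 0.975. For comparison, a paired t test at 1.02 with SD of change 1 (assumed) would reach 80% power with 10 patients in one arm (9.64 rounded up). The stated 20 per arm suits a two-group comparison.

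**3. What if before/after results were misread?** Suppose both arms truly fall by the same amount, so there is no treatment difference. Let p be the power of the paired t test in one arm of 20 (one-sample noncentral t, two-sided 5%). The arms are independent, so P(significant in step-down, not in control) = p(1 − p). The SD of change is not in the documents. Taking it as √(2(1 − r)) with baseline SD 1 and r = 0.7, 0.5 and 0 (assumed) gives 0.77, 1.0 and 1.41.

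| Equal fall (assumed) | SD 0.77 | SD 1.0 | SD 1.41 |
|---|---|---|---|
| 0.5: p | 0.787 | 0.565 | 0.325 |
| 0.5: p(1 − p) | 0.168 | 0.246 | 0.219 |
| 0.3: p(1 − p) | 0.236 | 0.186 | 0.126 |

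The range is about 13% to 25%. The between-arm test rejects in 5% of such trials, 2.5% in step-down's favour. The larger rates are false claims only if someone infers superiority from significance in one arm.

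**4. Does the planned decline create a further problem?** With SD of change 1, the step-down paired test is positive in at least 99% of trials at 1.02 or 1.275. The chance that it is positive while the between-arm test is not must then lie close to the between-arm type II error. For a decline of 1.02, simulation gives:

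| Control fall (assumed) | Paired positive, between-arm not | 1 − between-arm power |
|---|---|---|
| 0 | 0.111 | 1 − 0.882 = 0.118 |
| 0.3 | 0.390 | 1 − 0.602 = 0.398 |
| 0.5 | 0.63 | 1 − 0.361 = 0.639 |

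The columns differ by no more than about 0.01. These figures measure power lost if control improves, and a sentence about the role of paired tests would alter none of them.

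**The case for a change.** The strongest case for a change is that the gap is real and almost free to close. No sentence names the primary contrast or the role of the paired tests. Both arms can be expected to fall, so discordant results are not rare. A statement made in advance fixes which result answers the question, whereas one made after the data are seen looks chosen to suit them. Two or three sentences would do it, with no change to design, data or tests.

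The textual part of this stands: the sentence is missing, and writing it would be harmless. What does not stand is that its absence puts the result at risk. An analyst following the plan would run the unpaired t test, or the rank sum test, between the two arms and report the paired tests as additional description. The 13% to 25% range belongs to a decision rule found nowhere in the plan, and the discordance under the planned decline is ordinary type II error.

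The missing control-arm change is a separate matter of sample size. Under an assumed control fall of 0.5, power at a decline of 1.02 drops from 0.882 to 0.361. That point should be judged on its own and lends no weight to this one.

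**Conclusion.** No change is needed. The wording is incomplete, but the question, the design, the sizing and the named tests together identify the between-arm difference in A1c change from baseline to week 16 as the primary comparison, with the before/after tests as additions. Carrying out the plan as written gives a valid randomised comparison. Its 5% error rate is unaffected by the paired tests, and its power is unchanged: 88% at 1.02 points and 98% at 1.275, assuming SD 1 and no change in control.

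The only cost found, about 13% to 25% for a significant result in step-down alone, rests on assumed equal falls of 0.3 to 0.5 points, an assumed SD of change of 0.77 to 1.41, and a misuse that the plan does not propose. Naming the contrast explicitly is an optional clarification that would alter no planned test, error rate or power.

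### Within-arm paired tests on A1c cannot be read as treatment effects when entry requires A1c above 8% and the plan does not say which reading is the baseline

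*Combined protocol and SAP*

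**What the plan says.** The Inclusion criteria set a lower limit on A1c (above 8%) but give no date or source for the qualifying value. Under Procedures there are three visits, at the start, week 4 and week 16, with no separate screening visit or run-in. A1c is taken every time: "At each visit, all patients will have a blood test for A1c". Treatment changes start at the same visit as the first of these tests: "At first visit, the following changes will be made in intervention group". Control patients are advised to titrate basal insulin with the same self-titration scheme as the intervention arm.

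Outcome measurements defines the endpoint as follows: "The primary outcome is the change in A1c at the end of study period at week 16". It does not name a between-arm contrast.

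Statistical Analysis sizes the trial for a comparison of two independent groups and lists between-group tests first. It sets the general rule "Significance testing will be conducted at the two-sided 5% level" and then adds "before/after comparisons will also be performed on the same study patients, we will utilize paired t tests", together with McNemar's test. It does not say which variables the paired tests cover, whether they are descriptive, or what may be concluded from them. Regression to the mean is not mentioned.

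**The concern.** The entry limit selects on the outcome variable in one direction. A patient whose reading is above 8% partly through short-term variation or measurement error will tend to read lower next time. If the selected reading is then used as the before value, the expected change is negative with no treatment effect. A paired t test compares the mean change with zero, so it will reject more than 5% of the time when nothing has been achieved.

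At stake is the interpretation of within-arm p-values in a small open-label trial. A significant fall could be credited to step-down, or to insulin titration in the control arm, when part or all of it comes from selection. The control arm is the more exposed, because a modest fall there is easier to confuse with a selection effect of a few tenths of a point.

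**Working it through.** **The plan's own figures.** The plan gives no figure for the paired tests. Its only computed figure is the sample size: "We will attempt to recruit and consent 20 patients in each arm". Reading the anticipated 12-15% decline as relative to a mean of 8.5, the planned effect is 0.12 × 8.5 = 1.02 to 0.15 × 8.5 = 1.275 points. With SD 1, n per arm = 2 × (1.960 + 0.842)² / δ² = 15.7 / 1.02² = 15.1, so 16 (17 with the t distribution), and 15.7 / 1.275² = 9.7, so 10 (11 with t). The stated 20 is not reproduced exactly, but it exceeds what these inputs need. It is not at issue here and is used below as given.

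**Inputs.** From the documents: threshold 8, 20 patients per arm, two-sided 5% level. Assumed, because the documents do not give them: a normal source population with SD 1 and mean 8.0-9.5, and a correlation ρ of 0.7-0.9 between baseline and week 16. The stated mean of 8.5 with SD 1 does not fix the source: it is described as the value at study start, yet truncating a normal population of mean 8.5 and SD 1 at 8 gives an enrolled mean of 9.0 and SD 0.70. Hence the range.

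**Case 1: the qualifying reading is the baseline.** With no treatment effect and no time trend, the expected fall is (1 − ρ) × SD × φ(c) / (1 − Φ(c)), where c = (8 − mean) / SD. For mean 8.5, c = −0.5 and the ratio is 0.352 / 0.691 = 0.509, so the fall is 0.1 × 0.509 = 0.05 at ρ = 0.9 and 0.3 × 0.509 = 0.15 at ρ = 0.7. Rejection rates come from 20,000 simulated null trials per setting, with a paired t test in each arm of 20.

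| Source mean | φ/(1−Φ) | Fall, ρ = 0.9 | Rejects | Fall, ρ = 0.7 | Rejects |
|---|---|---|---|---|---|
| 8.0 | 0.798 | 0.08 | 12% | 0.24 | 28% |
| 8.5 | 0.509 | 0.05 | 8% | 0.15 | 14% |
| 9.0 | 0.288 | 0.03 | 6% | 0.09 | 8% |
| 9.5 | 0.139 | 0.01 | 5% | 0.04 | 5% |

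Over this grid, at least one of the two arms shows a significant fall in about 7-48% of null trials. Lower source means or lower correlations would give more.

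**Case 2: a separate first-visit reading is the baseline.** If its error is independent of the qualifying reading, the mean change is 0.00 and the paired test rejects in 4.9-5.1% of null trials (source mean 8.5). If correlation instead decays with time (first-order autoregressive, qualifying to baseline 0.8-0.9, baseline to week 16 0.7-0.9), some bias remains: rejection is about 7-12% for source mean 8.5 and 9-24% for 8.0.

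**Between-arm test.** A two-sample t test on change rejects in 4.7-5.5% of null trials in every setting, since selection acts equally on both randomised arms.

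**The case against.** A reader might infer that the paired tests simply do not have their 5% level. The documents do not support that, for two reasons. First, the inflation needs the qualifying A1c to be the baseline, or to share correlated error with it. The plan leaves this open, and a qualifying value taken from earlier records is compatible with the text. Second, a paired t test remains a valid test of zero mean change. Regression to the mean is a real change in the enrolled group, so the error lies in attributing it to treatment. The plan does not make that attribution, but it does not bar it either.

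A reader might also infer that the trial's main conclusion is compromised. It is not: allocation is randomised 1:1, the sizing is for two independent groups, the paired tests are additional, and the between-arm test keeps its level.

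On size, the objection is largely right. The title describes chronically poorly controlled patients, so higher source means are plausible, and at 9.0-9.5 the rejection rate is only about 5-8%. Even the largest fall in the table is 0.24 / 1.02 = 24% of the smallest planned effect. Nor does the problem extend to outcomes unrelated to A1c. Fasting glucose has no entry limit of its own and is included only because it can be expected to move with A1c; no separate calculation was made for it.

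What stands is that nothing in the plan prevents a within-arm p-value from being presented as efficacy. The anticipated decline is stated only for the treatment group, which invites that reading. Even without selection, a within-arm fall could not isolate the regimen, because basal insulin is titrated in both arms.

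**Conclusion.** The point holds in conditional form. With entry restricted to A1c above 8% and the baseline reading undefined, a significant within-arm change in A1c cannot be taken as a treatment effect in either arm. If the qualifying reading is the baseline, the spurious fall is about 0.01-0.24 points and per-arm rejection under no effect is about 5-28%, for assumed source means of 8.0-9.5, SD 1 and correlations of 0.7-0.9. With a separate first-visit baseline and independent error, rejection is about 5%; with correlated error, part of the excess remains. The documents do not settle which case applies. The effect is small against the planned decline and leaves the randomised comparison intact. It is a matter of interpreting secondary analyses, worth correcting because the correction is simple.

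**What to change.** In Statistical Analysis, make three changes:

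- Report within-arm changes in A1c and fasting glucose as mean change with 95% CI, labelled descriptive and without p-values, noting that they may include regression to the mean.
- State that efficacy claims rest only on the between-arm difference in change at week 16.
- Take the baseline A1c from the first-visit test, and state whether that test is separate from the qualifying value.

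The cost is a few sentences and the loss of the within-arm p-values for these two variables. The sample size, visits and randomised comparison are unchanged.
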